2.2. State of the art

The increased fracture burden in diabetes might partially be explained by an increased risk of falls and by alteration in the fall mechanism. A meta-analysis by Yang et. al. ¹⁵ showed that older persons with diabetes has increased risk of falls compared with healthy controls. Several risk factors that contribute to falls in diabetes exists. These include impaired postural control and gait, diabetic neuropathy, impaired vision, vestibular disorder, cardiovascular disease, comorbidity including hypertension, drugs and hypoglycemia¹⁶. Furthermore, patients with T2D has a higher risk of sarcopenia¹⁷ and decreased muscle function¹⁸, which has been proposed as a contributor to increased fall tendency¹⁹ and increased risk of fractures²⁰. Several studies of diabetes and fracture risk have included data on falls. In these studies, higher fracture risk associated with T2D persisted even after adjustment for increased frequency of falls²¹⁻²³. This suggest that additional underlying mechanisms such as decreased bone quality is involved in the increased fracture risk in T2D. Bone quality is affected by bone mass, bone turnover and bone material properties.

It is suggested that advanced glycation end products (AGEs) produced in response to hyperglycemia are incorporated in the bone structure, hence reducing the material and biomechanical properties of bone by stiffening the bone collagen and reducing bone strength²⁴. Furthermore, the hyperglycemia triggers hypermineralization in the bone causing high BMD²⁵. The interplay between bone and glucose metabolism is complex and not fully understood. An interaction is present between osteocalcin, which is a bone formation marker, but also interacts with insulin sensitivity, thus forming a bone-beta-cell axis^{26,27}. T2D is associated with decreased bone turnover caused by osteocyte dysfunction^{28,29}. It has been suggested that the low bone turnover in T2D cause microcracks, thereby increasing fracture risk³⁰. Bone Material Strength index (BMSi) is measured by microindentation and is reported to be decreased in T2D^{31,32}, which is considered to reflect decreased ability of bone to resist microcrack generation and propagation³³.

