Shanbhoug et al.⁴⁵ found that the observed cortical deficits were a characteristic of the T2D patients with microvascular complications rather than all T2D patients. However, the study was not able to perform an adequate assessment of the separate roles and severity of neuropathy, retinopathy, and nephropathy in bone structure due to limited sample size. A meta-analysis by Liu et al.⁴⁷ reported that T2D patients with diabetic neuropathy have an increased risk of developing osteoporosis and fragility fractures with an OR of 2.15 (95% CI 1.56-2.97). Contrastingly, a Danish study by Khan et al.⁴⁸ using patients enrolled in the Danish Center for Strategic Research in Type 2 Diabetes (DD2) cohort were not able to find a significant association between diabetic neuropathy and fractures. However, they did find an increased risk of falling. A well-powered retrospective study by Lee et. al⁴⁹ found that older male Veterans with diabetes (>98% had T2D) have an increased risk of any fractures and hip fractures, and diabetic neuropathy was reported to be the most important mediator of fracture risk observed in their cohort. A histomorphometry study in humans with high bone turnover showed that the nerve profiles density was 5-fold higher in the intracortical pores compared to bone marrow and periosteum, and the authors suggest an anatomical link between innervation and bone remodeling⁵⁰. Overall, there seems to be a higher fracture risk in subjects with T2D and diabetic neuropathy, which is a very common complication of T2D. However, the exact mechanisms behind this remain to be elucidated.

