3. STUDY OBJECTIVES

We hypothesize that a crosstalk between beta cells, bone-, nerve-, muscle- and fat tissues exists, and our main goal is to attain a better understanding of these relations and describe the T2D bone phenotype.

Hence, our aims are to:

- Compare bone microarchitecture, bone biomechanical competence, and bone turnover markers in T2D with and without fractures.
- Examine how different phenotypes of diabetic neuropathy affects bone microarchitecture, bone material strength and bone turnover markers as well as postural control and physical function.
- To examine how insulin resistance effects bone microarchitecture, bone material strength and bone turnover.
- To examine the relationship between T2D phenotype (classical/insulinopenic/hyperinsulinemic or SIDD [severe insulin deficient diabetes]/SIRD [severe insulin resistant diabetes]/MOD [mild obesity-related diabetes]/MARD [mild age-related diabetes]) and body composition (fat and muscle mass and fat distribution, i.e. visceral adipose tissue)
- To investigate how microvascular complications (neuropathy, retinopathy, and nephropathy) are affected by T2D phenotype (classical/insulinopenic/hyperinsulinemic or SIDD/SIRD/MOD/MARD)

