Subjects will be tested standing on a force platform (Plux Biosignals S.A, Arruda dos Vinhos, Portugal) during quiet bipedal stance in four different sensory conditions each of 35 seconds: i) eyes open, standing on a firm surface, ii) eyes closed on firm surface, iii) eyes open on soft surface, iv) eyes closed on soft surface. The trial including four sensory conditions will be recorded in one sequence and repeated two times separated by short breaks (30-60 s) in between. Subjects are asked to stand in the middle of the force platform as quiet as possible. All tests are performed barefoot, and the feet position is marked on the platform itself and on the soft foam pillow, during soft surface conditions. Soft foam pillow characteristics are: 48x40x6 cm (length, width, height), density 87 kg*m⁻³ (O'live Balance pad, Denmark). If subjects cannot hold their feet close together during the test, the distance between the widest spacing of the inner feet is measured and verified before all trials. Subjects are allowed a maximum of three attempts for each sensory condition. However, if they fail to complete the full 35 seconds of recordings in either of these attempts, this particular condition is skipped and not included in the analysis.

The vertical forces are extracted from the force platform (sampling rate at 1 kHz, Open Signals v. 1.2.8). The Center of Pressure (CoP) position versus time is extracted The Math Works, Inc., Natick, Massachusetts,

United States of America. First and last 2.5 seconds are excluded after low pass filtering (15 Hz Butterworth, 2nd order and zero lag). The CoP range and velocity, Anterior-Posterior (AP) and Medial-Lateral (ML) directions, are calculated for each sensory condition. Average parameters from the three trials, for each of the four sensory conditions are used for analysis. The coefficient of variation for the four different conditions is extracted in a pilot study of seven healthy adults (aged 24-31years) and is <8.1% for both CoP range and mean velocity. Both CoP range and mean velocity are extracted in the 30s analysis window. The CoP range is extract subtracting the maximum value by the minimum CoP position and the mean velocity is calculated dividing the total CoP displacement by it respective time window (30s).

Estimated time: 10-15 min.

Assessment of gait function

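### A balance condition not held for 35 s is left out of the analysis and never scored, which could slightly attenuate a neuropathy contrast in sway; the attempt and averaging rule also needs clarifying

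*Protocol*

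**What the plan says.** The second aim in Section 3 asks how phenotypes of diabetic neuropathy affect "bone microarchitecture, bone material strength and bone turnover markers as well as postural control and physical function". Sway is measured in four sensory conditions (Section 4.5, Test for postural control). On repetition, the sequence of four conditions "will be recorded in one sequence and repeated two times separated by short breaks". On attempts: "Subjects are allowed a maximum of three attempts for each sensory condition". On failure: if participants "fail to complete the full 35 seconds of recordings in either of these attempts", then "this particular condition is skipped and not included in the analysis". On the analysed value: "Average parameters from the three trials, for each of the four sensory conditions are used for analysis".

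No other section gives a failed condition a score or a rank. Section 6.4 leaves missing values out of the analysis. Section 8 notes in general terms that some participants may not complete every test. Section 6.2 offers t-tests, multiple regression and non-parametric methods.

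**The concern.** Two things are at issue.

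First, the loss depends on the outcome. A participant who cannot stand for 35 s on foam with eyes closed has the worst postural control in the study, yet contributes nothing for that condition. The background in Section 2.2 lists among the risk factors for falls in diabetes: "These include impaired postural control and gait, diabetic neuropathy, impaired vision". It also says of a Danish cohort study of diabetic neuropathy: "However, they did find an increased risk of falling". If failures fall more heavily on N+ (n = 40) than on F-/N- (n = 160), the participants who remain look more alike than the groups really are. A non-parametric test cannot repair this, because the values are removed before ranking.

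Second, the rule cannot be applied in only one way. The trigger uses a word for two alternatives where up to three attempts are allowed. It is not said whether attempts are the averaged trials or retries within a trial, and a mean of three trials is not defined for someone who completes one or two. Two assessors could follow the text and produce different datasets.

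**Working it through.** **Inputs from the protocol.** Group sizes are 160 (F-/N-) and 40 (N+), from Section 4.2. Up to three attempts are allowed and three trials are averaged (Section 4.5). The protocol gives no failure rate, sway SD or sway effect, so there is no figure of its own to reproduce.

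**Assumptions.** Sway has SD 1 and differs by 0.5 SD between N+ and F-/N-. For scale, the difference detectable with 80% power at two-sided 5% is (1.960 + 0.842) × √(1/160 + 1/40) = 0.495 SD. A latent instability has correlation r with sway and is shifted by s in N+. A participant fails when instability exceeds a common threshold c. A share p of F-/N- fails all permitted attempts.

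**Step 1: raw difference left among completers.** With c = z(1−p), the mean instability of completers, each measured from its own group's mean, is

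- m0 = −φ(c)/Φ(c) in F-/N-
- m1 = −φ(c−s)/Φ(c−s) in N+

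The retained share is [0.5 + r(m1 − m0)]/0.5.

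With s = 0.5:

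| p in F-/N- | c | Failing in N+ | m0 | m1 | r = 0 | r = 0.3 | r = 0.6 | r = 0.8 |
|---|---|---|---|---|---|---|---|---|
| 1% | 2.326 | 3.4% (1.4 of 40) | −0.027 | −0.078 | 100% | 97% | 93.9% | 91.8% |
| 2% | 2.054 | 6.0% (2.4 of 40) | −0.049 | −0.127 | 100% | 95% | 90.7% | 87.6% |

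Example for 2% and r = 0.8: [0.5 + 0.8 × (−0.127 + 0.049)]/0.5 ≈ 0.876. The raw loss is therefore 0-12%. Divided by the completers' pooled SD, the retained share at r = 0.6-0.8 is 94-95% (p = 1%) and 91-93% (p = 2%). Simulated t-test power (8,000 runs per cell) at r = 0.6-0.8 is 75% and 72% for completers, against 80-81% with complete data and 78-79% with failures given the worst rank.

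**Step 2: sensitivity.** With s = 0.25 and the sway difference kept at 0.5 SD, the raw share at r = 0.6-0.8 is 97-98% (p = 1%) and 95-96% (p = 2%). In the other direction, if failure rates are simply set at 5% in F-/N- and 20% in N+ with r = 0.5, simulation gives a loss of 24%. Nothing in the protocol supports rates that high. If failure were commoner in F-/N-, m1 − m0 would be positive and the difference would be inflated.

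**Step 3: any failed attempt against all attempts failed.** With independent attempts and a 20% chance of failing each, the first reading drops 1 − 0.8³ = 48.8% of participants and the second 0.2³ = 0.8%. Attempts by one person are not independent, so the same question was put with a between-attempt correlation of 0.7, solving for the threshold at which 1% or 2% of F-/N- fail all three. That implies 4.5% or 7.5% of F-/N- failing each attempt. With s = 0.5:

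| | F-/N- | N+ |
|---|---|---|
| Fail all three | 1% / 2% | 3.7% / 6.5% |
| Fail at least one | 9% / 15% | 22% / 30% |
| Complete only one or two | 8.4% / 12.7% (13 / 20 of 160) | 17.9% / 23.8% (7 / 10 of 40) |

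The last row is the group with no defined three-trial average if attempts are the trials. Over between-attempt correlations of 0.5-0.9 it ranges from 3-23% in F-/N- and 7-38% in N+. The range is wide, but the average is undefined whatever the rate.

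**The case against.** The case for leaving the rule alone is fair in several respects. A failed condition has no 30 s centre-of-pressure value comparable with the others, so leaving it out of a mean is understandable. Supplementary analyses of non-completion are often left to a statistical analysis plan, which is not at hand. A wider stance is accepted, loss is per condition, and exclusion criteria 9 and 17-20 (reduced physical ability, non-diabetic neuropathy, peripheral arterial disease, foot ulcers, amputation) remove many likely non-completers. N+ also admits participants with autonomic neuropathy and no severe vibration loss. The timed up-and-go, chair-stand and gait-speed tests are untouched. All of this stands, and it keeps the point small.

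It does not remove the point. The exclusion is a stated rule of the protocol, not a detail left open, and the limitation in Section 8 does not recognise loss that depends on the outcome.

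Three stronger readings are tempting and not supported:

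- A reader might infer that failures go unrecorded or unreported. The text only excludes them from the analysis. A published n per condition would show the loss, though not its reason.
- A reader might take commoner failure in N+, and hence attenuation, as established. The background concerns falls and fall risk factors, not the ability to hold quiet two-legged stance for 35 s. The N+ against F-/N- sway comparison is itself inferred from the second aim, not named as a planned test.
- A reader might see two runs contradicting three trials. One run repeated twice makes three, so this is an ambiguity only.

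**Conclusion.** The point holds as a minor one. The protocol removes the extreme of an outcome it sets out to study and gives that failure no score. A completers-only neuropathy contrast could therefore be attenuated, illustratively by 0-12% of the raw difference when 1-2% of F-/N- fail all attempts. That size rests wholly on assumed failure rates, a 0.5 SD shift in both sway and instability, and a sway-failure correlation of 0-0.8. It is zero when failure is unrelated to sway, and the direction is likely but not certain.

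The wording gap needs no assumption. The trigger does not fit three attempts, the link between attempts and trials is unstated, and the average is undefined after partial completion. Failure of all permitted attempts is the natural reading. Reading the trigger as any one failed attempt would drop far more participants, 22-30% of N+ against about 4-7% in the illustration above.

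**What to change.** 1. Replace the trigger with an explicit one: a condition counts as not completed only if no permitted attempt reaches 35 s. State how attempts relate to the three averaged trials and how many completed trials an average needs.
2. Code the reason for each missing condition at the time of testing: loss of balance, pain, refusal or technical fault. It cannot be reliably reconstructed later.
3. Report completion of each condition by group.
4. Keep the completers-only centre-of-pressure analysis. Beside it, add a rank-based or ordinal analysis with the same covariates, in which loss-of-balance failures take the worst rank and technical losses stay missing.

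The cost is a few sentences and one coded field, with no new measurement. The downside is that the supplementary result mixes failure with sway and gives no effect in centre-of-pressure units, so it supports the completers analysis and does not replace it.

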5. DATA COLLECTION

Patient data will be collected using the EPJ. Physical data achieved doing the study will be stored in locked desks with locked doors. The door will be locked if the room is left empty. Computer equipment is borrowed

by the North Jutland Region and is password protected in accordance with current guidelines. E-mails will only be sent through encrypted servers and mails, also in accordance with current guidelines.

6. DATA ANALYSIS

6.1. Sample size considerations

The total number of individuals that will be recruited for the study is based on previous cross-sectional or exploratory studies on diabetes, skeletal parameters, neuropathy, fall risk and postural control^{45,46,79}. The primary concern was to assemble a study population large enough to permit multiple testing. Therefore, by applying a risk of 5% for type 1 errors (2α) and a risk of 20% for type 2 errors (β), we estimated that 300 people with T2D divided into the respective groups (F-/N-, F+ and N+) were acceptable for the procedures to avoid standard errors in analyses.

6.2. Statistical methodology

Mean and Standard deviation will be used as descriptive statistics for Gaussian distributed variables, median and 75 percentiles for skewed distributions. T-tests for two samples and multiple linear regression will be used for Gaussian distributed variables or variables who can be log-transformed. For non-Gaussian distributed variables non-parametric statistics will be used.

6.3. Statistical significance

We use a statistical significance level of $\alpha < 5\%$.

6.4. Missing data

Missing data, interpretation errors, coagulation defects are considered missing values and will not be included in the analysis. In this case, each sample requisition is numbered (N). Furthermore, samples that cannot be measured in numerical values are categorized as missing values.

6.5. Procedures in change

The procedures for change in original study plan are stated at publishing scientific material. Furthermore, the local scientific committee and GCP-units are notified as required of these changes.

7. DATA AND SAFETY MONITORING PLAN

7.1. Data

The project will be registered at the North Denmark Region Research Department according to the GDPR regulations. All sensitive data will be stored in either REDCap, on the protected server of Aalborg University Hospital or locally at DISK's in DXA and HR-pQCT machines. Data will be stored anonymized after termination of the project.

7.2. Establishing of biobanks

Research biobank

Blood will be stored in a research biobank for later analysis. The blood is cooled down to -80 degrees and stored. Blood is handled by the research bio. Med. Lab. Technologists to safekeeping of EthyleneDiamineTetraAcetic acid (EDTA)-full blood, EDTA plasma, lithium-heparin plasma and serum. Subjects will be asked permission for storage in the research biobank.

Biobank for future research projects

Subjects will be asked permission to store an additional blood sample of 24 ml blood as well as an additional 8 ml urine sample from the 24-hour urine sample in a separate biobank with the perspectives of conducting future research projects. Only around 10 % of the tissue from skin biopsies is used for analysis. If the subject consents, excess material will be transferred back to Aalborg for storage in the biobank for future research. If the subject does not consent, excess material will be destroyed after analysis. Subjects will receive separate written information material about the additional blood sample, urine sample and storage of the excess skin tissue and will have to sign a separate consent form. Material will be stored in the separate biobank for 15 years after project termination or until a subject wants it destroyed. Use of material from the separate biobank will require permission from the regional ethics committee. Data will be handled in accordance with GDPR.

The collected and stored material will be encrypted after the project has been terminated via a serial number which cannot be related to the test subject. This number can however be related to the test subject's data and will be handled confidentially. If the test subject decides so, the material will be destructed after project termination. The project is covered by the North Jutland Region joint directory. The material will be stored with opportunity of identification in accordance with the North Jutland Region joint directory. This will be linked to an identification number if the approval from the North Jutland Region joint directory expires before new ways of use have been tested.

The biobank will function as a database, where additional and potential important information can be collected. This database will be used in future studies. Reasons are:

- Some biomarkers are in such low concentration that it is uncertain to perform routine analysis. In time, technology will improve thus providing an opportunity for new and smarter ways of testing. Therefore, this is of great research potential that the samples are kept.
- Some biomarkers are not discovered and therefore not available doing the trial.

There are found no risks associated with storage of these samples in the biobank.

8. STUDY LIMITATIONS

Some limitations must be considered in this study. First, all participants may not be able to complete all test procedures due to individual restrictions. Further, it is voluntary if subjects want to participate in skin biopsies, which is a limitation. Both PTT and QST require cooperation from the subjects and include subjective measures of pain. As the measured thresholds are not purely objective, psychosocial factors might influence test results.

9. ETHICAL CONSIDERATIONS

The trial will be conducted in compliance with *Harmonised Tripartite Guideline for Good Clinical Practice (ICH GCP)*⁸⁴ and applicable regulatory requirements, and in accordance with the Helsinki Declaration⁸⁵ for biomedical research involving test subjects. The methods used have been tested and performed in several studies both in Denmark and abroad and no long-term side effects have been reported. The risks associated

with the project are few as low dose radiation is used and the tests imply limited risks. The potential benefits in terms of well-being are large and are estimated to outweigh the potential risks.

9.1. Informed consent

Subjects interested in participating in the study will receive written information about the project ("Dine rettigheder som forsøgsperson i et sundhedsvidenskabelig forskningsprojekt" produced by *Den National Videnskabsetiske Komité (NVK)*) and a folder of the study ("deltagerinformation"). If the subject is interested in participating in the project after reading the written information, they will be asked permission to access medical records for screening in accordance with the Danish law. Medical records will be assessed for information on comorbidities and diabetes complications, relevant diagnostic imaging, medications, and previous biochemistry to ensure the potential participant is suitable for inclusion. If suitable for inclusion after screening medical records, they will be invited for a personal meeting, where all details for the study will be outlined by the investigator or a delegated assistant. The subject will be informed about the opportunity to bring a lay representative in advance of the meeting. The meeting will take place in a closed room without any disturbances, e.g. phone calls. Subjects will be invited for an additional visit at our center to sign the informed consent (IC) form and further screening. After signing the IC, the subject will have blood samples taken for screening. Furthermore, we will assess status of neuropathy with questionnaires and physical examination including biothesiometry, NC-stat-DPNCheck, orthostatic blood pressure and Vagus test, and the subjects will receive equipment and instruction for the 24-hour urine sample to collect before the study day.

The subjects must be fully informed of their rights and responsibilities while participating in the trial as well as possible disadvantages of potential risks. The investigator must ensure the subject has ample time to come to a decision whether to participate in the trial. A voluntary, signed, and personal dated IC must be obtained from the subject before any trial-related activity. The responsibility for seeking IC must remain with the investigator, but the task may be delegated by the investigator to a medically qualified person, in accordance with local requirements. The IC must be signed and personally dated by the person who seeks the IC before any trial-related activity. Subjects will be informed that information given in relation to the project before signing the IC will be passed on to the investigator.

If information becomes available that may be relevant to the subjects willingness to continue participating in the trial, the investigator must inform the subject in a timely manner, and revised IC must be provided and a new IC must be obtained.

Participants have time for reflection and an additional informational meeting (with participating relatives etc.) will be scheduled.

The given information will include:

- That this a scientific project investigating the T2D bone phenotype and potential risk factors of diabetic bone disease including diabetic neuropathy.
- Information regarding the different tests involved including risks.
- That withdrawal from the project is possible at any time.
- That data collected will be published in an anonymized form, without any traces of personal data
- That data collected will be safely stored in accordance with the rules in force.

- The IC gives the investigator, the sponsor, and the sponsor's representatives as well as any supervisory authority direct access to obtain information in the patient's medical record, etc., including electronic medical records, in order to see information about the subject's health conditions, which is necessary as part of the implementation of the research project as well as for control purposes, including self-control, quality control and monitoring, which they are obliged to carry out.

